APL is an uncommon disease; however excellent treatment modalities are available with cure rates of 90%. Current trials that are changing the treatment schedules, adding new drugs, or withholding maintenance might only have a minimal impact on survival in the general population. The intervention that will increase population wide survival is decreasing early deaths. Treating oncologists, who are not routinely involved in the care of acute leukemia patients in smaller centers as well as in larger treatment centers, may not be familiar with the treatment or expected complications. Addressing these issues by educating these physicians and co-managing patients will help improve survival in a condition that has a very high chance of cure.

Patients that were managed using the simple algorithm (Appendix I) demonstrated remarkable improvement in the overall survival. More importantly, a network was established with other leukemia treatment centers in the catchment area and helped local oncologists manage patients and decreased the mortality to 6.9% in 143 patients managed thus far. By replicating these results across a much wider population under the ECOG-ACRIN umbrella with additional sites, it is expected that adherence to the treatment guidelines and consultation with APL experts will reduce mortality rates even more than what previous trials have shown.

Seven of the ten deaths in our experience was in elderly population and although this is significantly better than published literature that suggests non clinical trial deaths to be as high as 50-60% in the same age groups, it shows that patients above the age of 60 years need a different approach. In our approach which is similar to the published literature from Chinese experience, using lower doses or single agent ATRA might lead to better outcomes even in this high risk population.

If the study is positive, efforts will be made to implement the concept nationally and manage APL patients with use of the streamlined guidelines and expert

support. A complement of experts is required to be made available permanently and the model should be followed for this project to be sustainable.

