Users that have not previously activated their iMedidata/Rave account at the time of initial site registration approval for the study in RSS will also receive a separate invitation from iMedidata to activate their account. Account activation instructions are located on the CTSU website, Rave tab under the Rave resource materials (Medidata Account Activation and Study Invitation Acceptance). Additional information on iMedidata/Rave is available on the CTSU members' website under the Rave tab at www.ctsu.org/RAVE/ or by contacting the CTSU Help Desk at [name] or by e-mail at [contact].

5. Methodology Plan

There will be 7 investigators accruing at 6 different centers (LEAD SITES) who will serve as the APL experts for this proposal. The patients treated at these 6 centers will be enrolled at their particular institution. **The study will not be open at other academic centers.** The APL expert at each site will either manage the patient or provide consultative oversight to the treating team. The sub-investigators at lead sites can consent patients but it is expected that the local PI will provide oversight. We expect to enroll a maximum of 30% of the patients at these lead sites. Induction mortality is a problem in larger centers as well from extensive data that has been published. We postulate that using the guidelines along with expert input will improve outcome in lead sites. This will give us the opportunity to assess the problem as well as outcome in academic centers and compare the results to community centers. Since the accrual goal is 200 patients over a 4 year period, the accrual at lead centers will be limited to 60 patients over a 4-year period (30%). The Study Chair and ECOG-ACRIN office will monitor this closely and once the target is achieved, enrollment at lead sites will be put on hold. Investigators from the LEAD sites will meet or have a conference call twice a year to discuss the progress and results.

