7.3.2 Secondary Objectives

Using the method of Kaplan-Meier, overall survival (OS) data will be described. The median OS and one-year OS rate will be estimated and 95% CI will be provided.

We confirm that the primary objective is to assess one-month mortality rate among all cases. Secondary analysis will involve evaluating outcome data in NCORP and academic sites separately. We clarified this further in Section [7.2](#). Overall the expected one-month mortality rate is in the range of 10-15% across all patients as well as in two subgroups of NCORP and academic sites.

With 200 (180 eligible) patients, we expect to build a confidence interval not wider than 11% for the expected one-month mortality rate of 10-15%. With 140 (126 eligible) cases from NCORP sites, the confidence interval for the one-month mortality rate will be not be wider than 13%.

For the safety endpoints, the severity and duration of coagulopathy, bleeding, infections and differentiation syndrome will be measured based on the CTC version 4.0. Analysis of the safety data will be mostly descriptive. The proportion of patients with the worst degree toxicity of grade 3 or higher will be assessed and presented with 95% CI. The length of hospital stay is defined as a period between the discharge and admission dates for the first hospitalization. For patients with no hospitalization, this will be defined as 0. To assess the associations between the length of hospital stay and toxicity measures (bleeding, infections, differentiation syndrome), each toxicity measures will be dichotomized as "mild" vs. "severe" and the length of hospital stay will be compared using the two-sample t-test.

The time from diagnosis and initiation of treatment will be assessed and dichotomized as "short" vs. "long" using the median value. One-month mortality rate will be compared in these two groups (short vs. long) using the Fisher's exact test. Overall-survival will also be

compared in these two groups using the logrank test. In this analysis, the time of diagnosis will be determined by both: i) confirmed diagnosis date and ii) date of suspicious APL. The dichotomized value of long vs. short based on the both times will be evaluated. Similarly the one-month morality rate and overall survival between the lead institutions and NCORP community centers will be compared. For all comparisons, two-sided p-values will be reported.

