Compliance with treatment guidelines will be assessed as binary outcome and the successful compliance rate will be described with 95% confidence interval. A regression model will be developed to evaluate the factors associated with outcome. Data items such as age, risk status, comorbidity will be collected and evaluated.

Rev. Add2

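### Lead sites and NCORP community centres are compared by unadjusted tests, and the planned regression on collected baseline factors is not tied to that comparison, so case mix can mimic or mask a centre effect

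*Combined protocol and SAP*

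**What the plan says.** Section 7.3.2 first splits patients at the median time from diagnosis to treatment. For mortality, "One-month mortality rate will be compared in these two groups (short vs. long) using the Fisher's exact test"; overall survival is "compared in these two groups using the logrank test". It then adds: "Similarly the one-month morality rate and overall survival between the lead institutions and NCORP community centers will be compared". No covariate, stratum or adjustment is named, and "For all comparisons, two-sided p-values will be reported".

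The same section goes on to plan a model: "A regression model will be developed to evaluate the factors associated with outcome". It adds: "Data items such as age, risk status, comorbidity will be collected and evaluated". The outcome, the form of the model and the list of terms are not given, and centre type is not mentioned.

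Section 5 (Methodology Plan) gives the purpose of including lead sites: to assess outcome in academic centres and "compare the results to community centers". Objective 2.2.4 asks for outcomes in the two centre types to be evaluated separately. Section 7.2 anticipates 54 eligible patients from lead sites and 126 from NCORP sites, keeps the primary analysis pooled over all sites, and calls analysis of the secondary endpoints mostly descriptive.

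**The concern.** The two centre types are not randomised groups. A patient is treated where he or she presents or is transferred. Section 1.1 itself says that advanced disease, socioeconomic constraints and distance can keep patients from reaching a large centre, which describes selection that may be related to prognosis. Section 1.3.1 says that age and comorbidity are not grounds for exclusion, so the mix within each centre type is unrestricted.

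The documents also point to age as prognostic. Section 1.1 gives a registry early death rate of 17.3% overall and 24% above age 55. Section 1.2 reports: "Seven of the ten deaths in our experience was in elderly population".

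If the mix differs by centre type, a crude test combines who was treated with how well they were treated. At stake is the contrast that section 5 sets out to make. A crude difference could be credited to centre expertise or held against community care, and a crude similarity could cover a real gap.

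**Working it through.** **1. The plan's own figures.** Sections 7.2 and 7.3 give power and intervals for each centre group against a fixed 30%, and none for one group against the other. The stated figures reproduce:
- NCORP, n = 126, exact one-sample binomial test of 30% against 15% at two-sided 0.05: reject at 27 or fewer deaths, power 98.0% (stated: at least 90%).
- Lead sites, n = 54: reject at 9 or fewer deaths, power 71.4% (stated: less than 80%).
- Exact 95% intervals: 13/126 gives 5.6-17.0%; 19/126 gives 9.3-22.5%; 5/54 gives 3.1-20.3% (stated 3-20.3%); 8/54 gives 6.6-27.1%.

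**2. What case mix alone could do.** The documents give no age distribution by centre type and no age-specific one-month mortality for this setting. These are therefore assumptions: mortality 25% at age 60 or over, 7% below, and no centre effect within either age group. With share s aged 60 or over, the crude rate is 25% × s + 7% × (1 − s).

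| Share aged 60 or over | Crude rate |
|---|---|
| 20% | 0.20 × 25 + 0.80 × 7 = 10.6% |
| 35% | 0.35 × 25 + 0.65 × 7 = 13.3% |
| 40% | 0.40 × 25 + 0.60 × 7 = 14.2% |

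- Lead 20%, NCORP 35-40%: NCORP looks worse by 13.3 − 10.6 = 2.7 to 14.2 − 10.6 = 3.6 points.
- Lead 35-40%, NCORP 20%: NCORP looks better by the same 2.7 to 3.6 points.
- Equal shares: difference 0.

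**3. Masking.** Assume mortality of 5% in low-risk and 25% in high-risk patients at lead sites, and a true NCORP odds ratio of 2 in each stratum, so NCORP mortality is 9.5% and 40%. With 50% high-risk at lead sites and 20% at NCORP sites:
- lead: 0.50 × 5 + 0.50 × 25 = 15.0%
- NCORP: 0.80 × 9.5 + 0.20 × 40 = 15.6%
- crude odds ratio: (0.156/0.844) / (0.150/0.850) = 1.05

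An odds ratio of 2 in every stratum would show as almost nothing.

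**4. Sensitivity to the assumed values.** With no centre effect, stratum mortality of 5/25%, 3/20% or 8/24%, and high-risk shares of 25 v 35%, 20 v 40% or 20 v 50% (lead v NCORP), the crude odds ratio runs from 1.15 to 1.90.

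**5. Power and precision of the planned test** (54 v 126, exact unconditional power of the two-sided Fisher test at 0.05; the 10-15% range is the plan's own expectation for both groups):
- lead 10%, NCORP 15%: power 10.6%
- lead 15%, NCORP 10%: power 14.1%
- 12% in both groups: rejection 3.7%
- age scenarios of step 2, 10.6% v 13.3% and 10.6% v 14.2%: rejection 5.4% and 6.9%

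The Wald 95% half-width of the difference is 1.96 × √(p₁(1−p₁)/54 + p₂(1−p₂)/126). For 10% v 15% this is 1.96 × √(0.00167 + 0.00101) = 10.1 points; for 15% v 10%, 1.96 × √(0.00236 + 0.00071) = 10.9 points.

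**6. Events available for adjustment.** 10-15% of 180 is 18-27 deaths. With centre, age, risk and comorbidity as one term each, that is 18/4 = 4.5 to 27/4 = 6.75 deaths per term.

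**The case against.** The strongest reply has four parts.

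- **The regression may already cover this.** It evaluates age, risk status and comorbidity, and nothing excludes centre type from it. This stands in part: much of the remedy is planned. But the text neither names centre type nor makes the model the basis of the centre comparison, whereas the crude comparison is stated.
- **Little harm can follow.** An artefact of 2.7-3.6 points lies well inside an interval of about ±10 points and raises Fisher rejection only from about 3.7% to 5.4-6.9%. The endpoint is secondary and the analysis mostly descriptive. This stands as to false significance. It does not remove bias from the point estimate, and a descriptive crude difference is confounded in the same way.
- **The prognostic evidence is thin.** The pilot count of deaths in elderly patients has no denominator, so no age-specific rate follows from it, and section 1.1 does not quantify selection. This stands, and it is why every case-mix figure above is an assumption.
- **Adjustment does not cure low power.** This also stands.

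A reader might infer that the comparison will be biased, or that the trial cannot show whether the strategy works in community centres. The documents support neither. They give no case mix by centre, so bias is possible and not established. Objective 2.2.4 asks for separate evaluation, and section 7.2 addresses the community question by testing NCORP mortality against 30%, with power that reproduces at 98%. Nor does any text say that a non-significant result would be read as equivalence; the plan merely gives no caution against it.

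**Conclusion.** The point holds in limited form. The lead-versus-NCORP contrast is specified only through crude tests on non-randomised groups, while the baseline items needed to adjust it are collected and sit in a regression that is not connected to it. Case mix can therefore create or conceal a centre difference. The direction and size are unknown: 2.7-3.6 points either way under the assumed age mortality and shares, and zero if the shares are equal. The practical risk is less a spurious significant result than over-reading a crude estimate, or a non-significant p-value from a test with about 11-14% power across the plan's own expected range. The pooled primary analysis and the NCORP analysis against 30% are not affected.

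**What to change.** In section 7.3.2, tie the planned regression to the centre comparison:

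- Enter centre type with prespecified age and risk group, adding comorbidity only if the number of deaths allows. Use penalised (Firth) logistic regression for one-month death and a Cox model for overall survival.
- Report the adjusted centre estimate with its 95% interval as the main comparison. Keep the crude Fisher and logrank results as descriptive support.
- Tabulate baseline characteristics by centre type.
- State that a non-significant result is not evidence of equal outcome, and give the power of the comparison.

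The cost is SAP wording and a small amount of analysis; no new data are needed. The drawback is that 18-27 deaths carry only two or three terms, so the adjusted estimate will still be imprecise, and factors that are unmeasured or left out of the model can still confound it. Fixing the terms before outcomes are examined by centre type also avoids choosing covariates after the fact.

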Appendix I

Acute Promyelocytic Leukemia Treatment Guidelines

Developed at Georgia Regents University, August 2013 Revised May 2017

AUTHORS: [name] [contact] Office: [contact]
[name] [contact] Office: [contact]

WORK-UP

BASELINE

- Chest X-ray
- Echocardiogram and EKG
- PICC line placement – NO central lines in chest or neck or invasive procedures (bronchoscopy, spinal tap, endoscopy)
- Bone marrow examination (aspirate, biopsy, flow, cytogenetics, FISH for t15:17, PCR for PML-RAR α). Day 14 marrow is **NOT** necessary.

DAILY

- CBC, CMP, PT, PTT, fibrinogen **TWICE DAILY** until lab & clinical coagulopathy is resolved. CMP daily and twice a day as dictated by clinical condition.
- D-dimer **ONCE DAILY** for **ENTIRE** hospitalization.

PREVENTION/TREATMENT OF COAGULOPATHY

- Intracranial, pulmonary and GI hemorrhages are frequent
- Risk of hemorrhage is ↑ with the presence of any of the following - active sites of bleeding, ↓ fibrinogen, ↑ D-dimers, ↑ PT & PTT, ↑ WBC, ↑ peripheral blasts, renal failure and poor performance status;

Rev. Add2

- **Keep platelets above 50,000 (until resolution of DIC)**
- If there are any active sites of bleeding on presentation (e.g., needle sticks, bone marrow biopsy sites,), and prolonged PT/PTT), give 4 units of fresh frozen plasma (FFP) at the start of ATRA and chemotherapy. **CONTINUE FFP support TWICE A DAY** until clinical bleeding resolves.

Rev. Add2

- **Keep fibrinogen above 150.** Use 10 units of cryoprecipitate if < 150 (until DIC resolves).
- When clinical & lab coagulopathy is resolved, blood product support is per standard guidelines.

→ APL IS A MEDICAL EMERGENCY - START ATRA ASAP ←

PREVENTION/TREATMENT OF APL DIFFERENTIATION SYNDROME

Differentiation Syndrome-symptoms are – dyspnea, unexplained fever, ↑ weight, peripheral edema, unexplained hypotension, acute renal failure, CHF, pleuro-pericardial effusions, and interstitial pulmonary infiltrates.

- Daily weights - **BEDSIDE SCALES ONLY**
- Keep I/O matched – **METICULOUSLY**

Rev. Add2

- Diuretics if increase in fluid retention or weight.
- Prednisone 0.5 to 1 mg/Kg in all patients for 2 weeks as prophylaxis starting on day 1 followed by a taper.
- Increase Dexamethasone to 10 mg IV BID from the prophylactic dose above, if onset of DS symptoms.
- If WBC > 10,000, dexamethasone 10 mg IV bid could be started on day 1 before initiating ATRA.
- Temporary discontinuation of ATRA or Arsenic Trioxide (ATO) is indicated only in case of severe cases of DS.
- Continue dexamethasone until 3 days after all symptoms are resolved. ATRA and/or arsenic can be resumed.

SUPPORTIVE CARE

- Allopurinol 300 mg daily.
- Antibiotic prophylaxis - levofloxacin 500 mg po daily or similar antibiotic.
- Antifungal prophylaxis - posaconazole 200 mg po 3 x3x daily, voriconazole 200 mg po 2 x2x daily, Micafungin 50 mg daily or a similar drug as per institutional standard.
- Anti-viral prophylaxis - acyclovir 400 mg po 2 x2x daily or valacyclovir 1000 mg PO daily.
- RBC transfusion recommended when HGB ↓ 8.

INDUCTION OF LOW AND INTERMEDIATE RISK PATIENTS WBC < 10,000 and PLTS < 40,000 -

- ATRA 45mg/m² in divided doses twice a day plus ATO 0.15 kg daily until complete hematologic remission (no anthracycline). Prednisone 0.5 mg/kg for 14 days followed by a gradual taper if no evidence of DS.
OR
- ATRA on Day 1 at 45 mg/m² DAILY in divided doses twice a day until complete hematologic remission.
- Idarubicin 12 mg/m² on Days 2, 4, 6 and 8. Prednisone 0.5 mg/kg for 14 days followed by a gradual taper if no evidence of DS.

Rev. Add2

INDUCTION OF HIGH RISK PATIENTS WBC > 10,000

- ATRA to be started as soon as diagnosis is suspected at 45 mg/m² in divided doses twice a day until complete hematologic remission.
- Idarubicin to be started on the SAME DAY OR AS SOON AS POSSIBLE WHEN THE DIAGNOSIS IS CONFIRMED at 12 mg/M² on days 1, 3, 5 and 7.
- Dexamethasone 10 mg IV bid on days 1 to 14 followed by a taper.
- Arsenic at 0.15 mg/Kg can be started on day 10.
- Even if the genetic results are not available, it is reasonable to start Idarubicin if the diagnosis is otherwise strongly suggested.

Rev. Add2

ARSENIC ADMINISTRATION

- Prednisone 0.5 mg/Kg from days 1-14 days followed by a taper. If high risk, dexamethasone 10 mg IV bid on days 1 to 14 followed by a taper.
- Watch for differentiation syndrome.

- Watch for prolonged QTc interval.
- Keep Mg above 2.0 and K above 4.0.
- Follow LFTs for grade 2 - 4 liver dysfunction. If this occurs HOLD arsenic.

SUGGESTED MANAGEMENT OF ATRA/ARSENIC-INDUCED LEUKOCYTOSIS

- WBC 5 - 50 K- Hydroxyurea 500 mg qid
- WBC > 50K- Hydroxyurea 1000 mg qid
- If leukocytosis does not resolve one or two doses of Idarubicin or Cytarabine could be considered.
- **NO LEUKOPHERESIS.**

ELDERLY PATIENTS / \geq 60 years AND PATIENTS WITH SEVERE COMORBID CONDITIONS

- May not be candidates for cytotoxic chemotherapy.
- Consider dose reduction of ATRA. Single agent and consider 25 mg/M2 for 14 days.
- Consider dose reduction of ATO and consider 0.075 mg/M2 and add on day 15.

A Simplified Patient Care Strategy to Decrease Early Deaths in Acute Promyelocytic Leukemia (APL)

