4. Follow treatment guidelines according to Appendix I. If necessary, deviations from guidelines may occur per discretion of treating physician and consulting physician.
5. 7 investigators at the lead sites have been identified as APL experts.
6. Consent patient after APL diagnosis is confirmed.

Rev. Add2

1. Introduction

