Appendix III

NCORP PROVIDER INFORMATION SHEET

This is a research study focused on decreasing induction mortality in Acute Promyelocytic Leukemia (APL). Historical data shows an induction mortality of 30% in the general population and the purpose of this study is to decrease it to < 15%. NCORP providers will be given this information sheet along with the treatment guidelines in Appendix I.

- A. The study will consist of using the simplified APL treatment algorithm that is attached.
- B. Equally important is for the provider at NCORP sites to call an APL expert listed in the protocol or the PI/Co-PI. Cell phone numbers of APL experts are in the Protocol.
- C. The APL expert will function as a resource during induction to prevent and manage complications. It is suggested that the provider at NCORP sites call the APL expert as frequently as needed during the first 4 weeks. The experts are available 24/7.
- D. NCORP providers will document discussion with the APL expert and clinical decisions in the Medical Record. APL experts will fill the Expert/NCORP Provider communication sheet.
- E. There are no obvious discomforts to the patient since the patient will be treated on the accepted standard of care. Expert support may help in preventing and managing complications and improving outcome.
- F. We will retain all patient records and signed informed consent forms filed in a secure location. Database is maintained using web-based database system. Only research members are granted access to web-based database system with user ID and password.
- G. Participation is voluntary and the patient may choose not to participate in the trial. In that case the patient will be treated per usual treatment guidelines. Participants may discontinue at any time without penalty or loss of benefits.

A Simplified Patient Care Strategy to Decrease Early Deaths in Acute Promyelocytic Leukemia (APL)

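### Appendix I prints the low/intermediate-risk arsenic trioxide dose as a mass in kilograms, which cannot be reconciled with its own high-risk line

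*Combined protocol and SAP*

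**What the plan says.** Appendix I offers two induction options for low- and intermediate-risk patients, separated by OR. The first combines ATRA with arsenic trioxide and words the arsenic part as "plus ATO 0.15 kg daily until complete hematologic remission (no anthracycline".

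Two other lines in the same appendix give an arsenic dose:

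- High-risk section: "Arsenic at 0.15 mg/Kg can be started on day 10".
- Section for patients aged 60 or over or with severe comorbidity: "Consider dose reduction of ATO and consider 0.075 mg/M2 and add on day 15".

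The block on arsenic administration covers steroid cover, QTc, electrolytes and liver function, but states no arsenic dose.

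The appendix is meant to be used. A note to the Schema instructs: "Follow treatment guidelines according to Appendix I". It then allows deviations at the discretion of the treating and consulting physicians. Section 3.1.2 makes acceptance of the guidelines an eligibility condition. Appendix III adds: "NCORP providers will be given this information sheet along with the treatment guidelines in Appendix I". Sections 3.1.3 and 5.2.1 ask for the expert call as early as possible, and at the latest 3 days after treatment has begun.

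**The concern.** A dosing line needs a drug unit, a body-size basis where the dose is scaled to the patient, and a frequency. The low/intermediate-risk line has a frequency, but its unit is the kilogram and it is scaled to nothing. Read literally, it sets one fixed amount for every patient. The high-risk line for the same drug uses the same digits with a different unit and a weight basis.

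The simplified guideline is one of the two components of the strategy tested under the primary objective (Section 2.1.1); expert support is the other. The intended readers include community oncologists who, by Section 1.2, may not know the treatment well. Because the expert call may follow the start of therapy by up to 3 days, a first arsenic dose could be ordered from the page alone. The reader would then have to infer the unit and the basis, with both a body-weight and a body-surface expression printed nearby.

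A lesser matter concerns compliance with the guidelines, a secondary endpoint analysed as a binary outcome (Sections 7.1 and 7.3.2). If arsenic dosing is part of that judgement, it cannot be scored against this line as printed.

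**Working it through.** This is a comparison of text and a unit conversion. No sample size, power, error rate or event count enters.

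**Step 1. Set every arsenic dose expression in Appendix I side by side.**

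| Place in Appendix I | As printed | Drug unit | Body-size basis | Frequency on the line |
|---|---|---|---|---|
| Low/intermediate risk, first option | 0.15 kg | kilogram | none | daily |
| High risk | 0.15 mg/Kg | milligram | body weight | none |
| Age 60 or over, or severe comorbidity | 0.075 mg/M2 | milligram | body surface | none |
| Arsenic administration block | no dose given | – | – | – |

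**Step 2. Convert the low/intermediate-risk line.** With 1 kg = 1,000,000 mg:

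0.15 kg × 1,000,000 mg/kg = 150,000 mg (150 g) per day, the same for every patient.

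**Step 3. Evaluate the high-risk line over a range of weights.** The documents give no body weights, so 50, 70 and 100 kg are assumptions. Dose = 0.15 mg/kg × weight; ratio = 150,000 mg ÷ dose.

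| Assumed weight | Dose from the high-risk line | Ratio |
|---|---|---|
| 50 kg | 0.15 × 50 = 7.5 mg | 150,000 ÷ 7.5 = 20,000 |
| 70 kg | 0.15 × 70 = 10.5 mg | 150,000 ÷ 10.5 ≈ 14,286 |
| 100 kg | 0.15 × 100 = 15 mg | 150,000 ÷ 15 = 10,000 |

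No plausible weight brings the two lines together. They are not two ways of writing one dose.

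**Step 4. Look for a line that settles the matter.** Section 5 refers treatment to the guidelines and leaves consolidation and maintenance to the treating physician. Section 6 refers tests and procedures to Appendix I. Neither states an arsenic dose. The line for elderly or comorbid patients is a suggested reduction on a different basis. It cannot be converted to a per-weight figure without a body surface area, which the documents do not give. The low/intermediate-risk expression therefore stands alone and uncorrected.

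**The case against.** The strongest objection is that the fault may lie in text extraction. The point turns on a few characters, and the text examined here, extracted from the PDF, is visibly damaged nearby: the frequencies in the antifungal and antiviral lines are garbled. This cannot be fully excluded. Two things make it unlikely. The visible damage repeats characters and does not drop them. A per-weight unit also survives later in the same option ("Prednisone 0.5 mg/kg for 14 days followed by a gradual taper if no evidence of DS") and again in the high-risk arsenic line. A look at the source PDF will settle it.

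A second objection is that safeguards exist. Deviations are permitted, Sections 5.1.2 and 5.2.1 accept that full adherence is not always feasible, Section 1.3.2 says treatment will not change from present standard of care, and expert contact is required. These lower the risk. They do not cure an instruction that cannot be carried out as printed, and the expert may be reached only after therapy has begun.

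A reader might also infer more than the documents support:

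- **That patients would receive 150 g.** The ratio of 10,000 to 20,000 shows that the literal reading is absurd. It says nothing about likely exposure, and an amount so large is conspicuous. The realistic hazard is guesswork about unit and basis.
- **That about two thirds of the trial is affected.** Section 1.2 reports one third high risk in a Latin American cohort, and (1 − 1/3) × 200 ≈ 133. That mix is not this trial's; the protocol states none. The line is also one of two alternatives, its heading is restricted by platelet count as well as white count, and elderly or comorbid patients have their own section.
- **That the high-risk arsenic line has no stopping point.** Section 5.5 gives a general one for induction, hematologic remission. What that line lacks is a frequency.
- **That the compliance endpoint is unworkable.** Section 7.3.2 names no dose criterion, so the documents do not show that this line decides compliance.

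**Conclusion.** The point holds, as an inconsistency of units in an operative dosing line. The low/intermediate-risk arsenic dose is an absolute mass in kilograms, the high-risk dose is in milligrams per kilogram without a frequency, and the dose for elderly or comorbid patients is on a body-surface basis. The first two cannot both be read as printed, and no other text states the dose for the low/intermediate group.

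The conclusion assumes that the source PDF carries the same words. The 50 to 100 kg range serves only to show scale, and the conclusion does not depend on it. How many patients the line could reach cannot be derived from the documents. The figures in Section 7 for sample size, power and confidence intervals are unaffected. No view is taken on which dose is right.

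Subject to the PDF check, this should be corrected before sites rely on Appendix I: it concerns a dose, in a guideline that itself calls the disease an emergency.

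**What to change.** 1. Confirm the wording of the low/intermediate-risk arsenic line in the source PDF.
2. If it is as quoted, have the guideline authors check it against their source and reconcile the three arsenic expressions in Appendix I, so that each carries a consistent drug unit, body-size basis and frequency. The values are theirs to confirm.
3. Reissue Appendix I to the lead sites and NCORP sites, marking the change, and replace the copy handed out with Appendix III.
4. If arsenic dosing is to count towards guideline compliance, state in Section 7.3.2 that it is judged against the corrected text.

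The cost is a short correction to the appendix and its redistribution. The design, the sample size and the primary analysis stay as they are.
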